## Programmatic data outcomes collected by PSI outreach sites

- Number of individuals who have self-tested in each community
- Number of people who linked to PSI outreach services
- Number of men taking up VMMC in each community
- Number assessed for ART
- Number initiated on ART
- Number taking up cervical cancer screening in each community
- Number of contraception consultations in each community

## Data obtained from government ART services

• In all health facilities within each district: number of ART initiations six months before HIVST kit distribution, during distribution, and three months after distribution

Pilot distribution of HIV self-test kits will be done at New Start static and mobile HIV testing and counselling centres and through VMMC services. Clients who seek testing at these facilities will be offered a choice between HIVST and PDHTC and we will measure uptake of HIVST and linkage to post-test services among self-testers.

## **4 DETAILED PROCEDURES**

## 4.1 Formative Work

Formative work that will inform the implementation of community-based kit distribution will be done according the study protocols that have been approved by MRCZ and UCL, references MRCZ/A/1801 and MRCZ/A/2023 for MRCZ; and 5367/001 for UCL.

## 4.1.2 Methods for detecting social harms during study implementation

A mapping exercise will be conducted in the study communities to determine the means for detecting /monitoring GBV in communities as well as the levels of support available for victims through the District AIDS Action Committees (DAAC). The mapping exercise described below will also take into account findings of the FGDs investigating the issue of social harms.

The study team will investigate what kind of support services including counselling and legal support are available for the victims and what data these agencies collect. In communities where services are inadequate or not available, discussions will be held with organisations in nearby communities and a referral system will be established to ensure that support is extended and that all study communities have access to GBV support services. Organisations operating within the relevant districts will be alerted of the study. On a monthly basis the study team will consult with the organisations to determine the number of GBV reports and underlying causes.

Participants will be given a toll-free number that they can call to discuss any concerns or questions they may have before, during and after self-testing. Participants will also be told to use this number if they need any support in the event that they have any difficulties after testing. While this will be for general questions and/or support, staff manning the line will actively document all reports on social harms as a result of the study. PSI will develop standard operating procedures to deal with these reports and assist victims of domestic violence. Staff manning the hotline will take action according to the standard operating procedures.

## **REFINING STUDY PROCEDURES FOLLOWING FORMATIVE RESEARCH**

Based on findings from formative work, the study team will refine procedures for facilitating and documenting linkage to prevention and care services.

## 4.2 TRIAL PROCEDURES

## 4.2.1 Site selection

The cluster randomised trial will be conducted in seven districts in five provinces in Zimbabwe.

- Mashonaland Central Province Mazowe
- Manicaland Province Buhera
- Masvingo Province Gutu, Masvingo, Chivi
- Midlands Province Gweru
- Matebelend South- Bulilima

Thirty-eight PSI outreach communities defined by local government as wards will be selected from across these seven districts. PSI outreach sites are located in rural communities, each serving a ward, and provide VMMC services and outreach HTC. Outreach communities included in the trial will be separated from each other by at least 20km (i.e. the outer border of a community is at least 20 km from the nearest point of another community) to minimise risk of contamination between communities.

In addition to the trial, PSI will continue to implement provider delivered HTC through outreach in 10 districts. Programmatic data collected from these 10 districts will also be analysed to explore the effects of provision of self-testing on HTC uptake.

## 4.2.2 Randomisation

Thirty-eight outreach communities in the seven study districts will be randomised in a 1:1ratio to receive incentives for CBDs or no incentives. Randomisation will be performed by the study statistician. Restricted randomisation will be used to minimise imbalance in key factors between arms (district, HIV prevalence and proximity to a health facility). A public randomisation ceremony will be held to select the final allocation from a randomly-generated list of acceptable allocations.

## 4.2.3 Distribution of self-test kits and PSI programme activities

HIV self-test kits will be distributed by CBDs to all households in the study communities. CBDs will ensure that each household receives a kit for each member of the household who is willing to test. At time of kit distribution, CBDs will give out appointment cards on which clients will document the intended date and time of performing the self-test. This will ensure that clients make a commitment to self-test (an intervention that previous research has proven effective in ensuring future uptake of health interventions [23, 24]). CBDs will inform clients of the date of the next PSI outreach visit, and encourage them to think about the time that they would like to attend the outreach clinic. The client will be asked to write this time on their card, which will help foster a commitment to attend post-test services. The card will have the CBD identity number, and clients will be asked to take it to the outreach clinic.

Once they have self-tested, clients/participants will be asked to complete a short results form and to return both the form and the used test kit in a sealed envelope to a drop-off point in the community. The used kits will be placed in locked boxes that will be kept at health facilities. In addition, CBDs will also keep locked drop-boxes where clients can deposit their used test kits. No client identifiers will be placed on the used test kits, although it will be possible to know which household the kit came from. On a weekly basis PSI will collect the sealed boxes. Only authorised PSI staff will have the keys to the drop boxes. A late read of results of the returned kits will be done to estimate HIV prevalence among the HIV self-testers.

One to two weeks after self-test kits have been distributed to households within a community, a PSI outreach team will visit the community to provide a comprehensive package of services packaged as 'well woman' and 'well man' services. These services will include client-initiated counselling and

testing (for those who opted not to self-test); confirmatory tests, post-test counselling, CD4 testing services and clinical staging for those who self-tested HIV positive; referral to government treatment services for those confirmed HIV positive, , TB screening and TB laboratory testing for symptomatic clients, STI screening, blood pressure and blood glucose testing with onward referral to government services as required. HIV negative men will be referred to the nearest voluntary medical male circumcision (VMMC) outreach team. Women, regardless of HIV status, will be able to access cervical cancer screening using VIAC, contraceptive advice and provision including long acting reversible contraceptive methods (LARC).

This outreach team will revisit the community 3-4 weeks later to provide a second opportunity for those who did not attend at the first visit to access services.

Community based distributors (CBDs)	PSI/Z mobile outreach

 
House-hold level distribution of HIV self-test kits in 44 (the first six are pilot, and the last 38 will be assessed in the trial) outreach communities
 
Distribute appointment cards with each client's intended date and time of self-testing
 
Provide support to self-testers as necessary including with the testing process if requested
 
Inform clients of the date of the next PSI outreach visit
 
	
 
Provision of comprehensive package of services - well-man and well-woman - 1-2 and 3-4 weeks after distribution of kits by CBDs 
 
Services include client- initiated HIV testing for both self-testers and non self-testers
 
Referral of all confirmed HIV positive clients to government treatment services for ART, OI treatment
 
 
 

Figure 3: Roles and responsibilities of CBDs and PSI/Z outreach

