## Primary Objective

• To determine whether incentivising community based distributors (CBDs) to support selftesters is effective in improving uptake of self-testing and linkage to post-test services

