## **3 OVERALL RESEARCH STRATEGY IN ZIMBABWE**

We plan to deliver HIV self-test kits to households in rural communities using communitybased distributors (CBDs). CBDs will be trained to provide assistance to help people self- test if requested /required. CBDs will encourage people who self-test to link to post-test services provided by PSI Zimbabwe in their communities at either 1-2 weeks or 3-4 weeks after self-test kit delivery (See figure 1). We propose to conduct a clusterrandomised trial in 38 rural outreach communities in order to

test whether incentivising community based distributors (CBDs) according to number of clients who attend outreach services at weeks 1-2 and weeks 3-4 after self-test kit delivery increases testing uptake and linkage to post-test services. Sites will be randomised to incentives for community based distributors (CBDs) to link self-testers to post-self-test care or no incentives. (See figure 2). Six weeks after the first PSI outreach visit, community-based surveys will be conducted in four randomly selected enumeration areas (EAs) in each outreach community. Survey participants will be asked about whether they were offered self-test kits, whether they used them and their linkage to post-test services. In addition, to verify self-reports dried blood blot (DBS) samples will be taken for testing for HIV, viral load, recent infection and ARV levels. Study outcomes will be assessed programmatically and through the survey.

Figure 2	2: Stud	y design						
38 PSI outreach sites Random allocation of 19 sites per arm								
CBDs deliver self tes	∳ st kits t	o rural households						
6								
CBDs incentivised to link self testers to care	Process E\ Program da	CBDs not incentivised to link self testers to care	4 EAs					
PSI provide post-test services 1-2 and 3-4 weeks post test distribution PSI provide post-test services 1-2 and 3-4 weeks post test distribution								
Primary outcome – measured through survey (not programme) % self-report linked to PSI/govt clinic for any reason								
Secondary outcomes – measured through survey (not programme) % who report self-testing % who linked to PSI % men taking up VMMC								
% self-report linked % initi	l for co ated on	nfirmatory testing ART	s per					

Before randomisation, formative work with the following aims will be conducted:

- I. Understanding client/user preferences for HIV self-testing services
- II. Maximising detection of social harms as a result of HIV self-testing

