## Primary outcome assessed in representative population based survey

• Proportion of individuals who report attending PSI outreach services or any health facility following HIV self-test kit distribution

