## 4.2.4 Description of study interventions

## Incentives for CBDs

During training, CBDs in communities that have been randomised to CBD incentives for linking selftesters to post-test services will be told that they will get a stipulated amount of money (20c) for each self-tester who attends the PSI outreach site after testing. Upon attendance at outreach sites, all clients who report having self-tested will be asked to show their self-completed appointment card (which bears the CBD identity number) to PSI staff. Staff will keep a log of clients that attend according to CBD in order to facilitate payment of the CBD. If a client has not brought their appointment card, they will be asked to provide the name of the CBD who supplied the self-test kit, which will be verified with CBD kit distribution records in that area before the CBD is credited with the attendance.

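### A visit made only to return a used kit to a health-facility box can count as primary-outcome linkage, so a difference between arms in self-testing uptake can appear as a difference in linkage.

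*Protocol*

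**What the plan says.** Protocol section 3 defines the primary outcome, measured in the household survey, as "Proportion of individuals who report attending PSI outreach services or any health facility following HIV self-test kit distribution". Figure 2 in the same section describes it as "self-report linked to PSI/govt clinic for any reason". Neither requires that a service be received.

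Section 4.2.3 asks each self-tester, in both arms, to "return both the form and the used test kit in a sealed envelope to a drop-off point in the community". It continues: "The used kits will be placed in locked boxes that will be kept at health facilities". A second route follows: "In addition, CBDs will also keep locked drop-boxes where clients can deposit their used test kits". Because the CBD boxes are introduced as an addition, the natural reading is that clients may also use the facility boxes.

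The primary objective in section 2 asks whether the incentive "is effective in improving uptake of self-testing and linkage to post-test services". Under section 4.2.4 the CBD is paid 20c "for each self-tester who attends the PSI outreach site after testing".

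The survey description in section 4.2.6 lists questions on the choice to link, the reasons for attending or not, and the experience. It does not say that the purpose of a visit is recorded or used in the outcome.

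**The concern.** Unrelated clinic visits are background noise that randomisation should balance. Kit-return visits are different in three ways: a trial procedure creates them, only self-testers make them, and self-testing happens after allocation and is itself something the incentive is meant to change. If the incentive raises self-testing, more people in that arm have a kit to return. Some of them will go to a clinic for that purpose alone and may report the visit. The primary outcome can then favour the incentive arm without any extra person having received a post-test service.

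This cannot be left to the analysis stage. If the survey does not record why the person went, kit-return visits cannot later be separated from linkage.

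**Working it through.** **Inputs from the Protocol (section 6).** c = 19 communities per arm, m = 200 respondents per community, coefficient of variation k = 0.3, linkage 10% v 15%. The significance level is not given with the table; I assume two-sided 5%.

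**Reproducing the stated power.** For an unmatched cluster trial with proportions p0 and p1,

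power = Φ( √[ (c − 1)(p1 − p0)² / V ] − 1.96 ), with V = [p0(1 − p0) + p1(1 − p1)]/m + k²(p0² + p1²).

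For 10% v 15%, V = (0.09 + 0.1275)/200 + 0.09 × (0.01 + 0.0225) = 0.0040125. The ratio is √(18 × 0.0025/0.0040125) = 3.349, and Φ(1.389) = 91.8%.

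| Control v intervention | Protocol | Recomputed |
|---|---|---|
| 10% v 15% | 92% | 91.8% |
| 5% v 7.5% | 83% | 83.3% |
| 14% v 20% | 87% | 87.2% |

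The sample size calculation is not in dispute.

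**The artefact.** Let true linkage be 10% in both arms, s0 and s1 the self-testing uptake in the control and incentive arms, and f the share of self-testers who return the kit at a facility and report that visit. I take f as the same in both arms and drop-off as independent of true linkage. Then

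measured outcome = 0.10 + 0.90 × s × f,

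spurious difference = 0.9 × f × (s1 − s0).

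Neither s nor f is in the Protocol, so the values below are assumptions. The last two columns give the chance of a significant result in the incentive's favour when linkage truly does not differ; the nominal value is 2.5%. The first applies k = 0.3 to the measured rate. The second lets wards vary in true linkage only (between-ward standard deviation 0.3 × 0.10 × (1 − s × f)).

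| Uptake | f | Measured outcome | Difference (points) | k on measured rate | k on linkage only |
|---|---|---|---|---|---|
| 40% v 50% | 5% | 11.80% v 12.25% | 0.45 | 5% | 6% |
| 40% v 50% | 10% | 13.6% v 14.5% | 0.9 | 8% | 11% |
| 40% v 50% | 20% | 17.2% v 19.0% | 1.8 | 14% | 29% |
| 40% v 60% | 5% | 11.8% v 12.7% | 0.9 | 9% | 11% |
| 40% v 60% | 10% | 13.6% v 15.4% | 1.8 | 19% | 30% |
| 40% v 60% | 20% | 17.2% v 20.8% | 3.6 | 40% | 80% |

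Worked example, 40% v 60% with f = 20%: 0.10 + 0.9 × 0.4 × 0.2 = 17.2% and 0.10 + 0.9 × 0.6 × 0.2 = 20.8%. V = 0.008092, √(18 × 0.036²/0.008092) = 1.698, and Φ(1.698 − 1.96) = 40%.

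If s1 = s0 or f = 0, the spurious difference is exactly zero. The difference does not depend on k; the rejection probabilities do.

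**Equal drop-off.** If a share d of residents in both arms makes a kit-return-only visit, the measured outcome is 1 − (1 − linkage)(1 − d). With between-ward variation in linkage only, power for 10% v 15% is 91%, 89% and 85% at d = 2%, 5% and 10%. That is modest dilution.

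**The case against.** The facility route may be minor. Kits are to go to a drop-off point in the community, CBDs visit every household and hold boxes, and section 1.4 lists distance and travel cost as barriers to reaching a clinic. Someone with only an envelope to hand in has an alternative to the trip. This stands, and is why f may be small; it does not make f zero.

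The respondent must also report the drop-off as attendance, and section 4.2.6 frames its questions around linking to services. The questionnaire is not shown and may discourage such reports. But the outcome as written does not exclude them.

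The incentive pays for attendance at outreach, not for self-testing or kit return, and kits go to all households in both arms. A 20-point rise in uptake with no movement in linkage is therefore an extreme case. That stands too. The 40% v 60% rows show how the artefact behaves and are not a forecast.

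The breadth of the outcome looks deliberate. That is a fair choice for genuine service visits, but it does not call for counting a visit that the trial's own logistics create.

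A reader might infer a severe loss of power even when drop-off is equal in the two arms. Applying k = 0.3 to the inflated rate would give 84%, 70% and 48% at d = 2%, 5% and 10%. Most of that fall comes from letting a constant drop-off rate enlarge the between-ward variation, for which the Protocol gives no basis, so those figures should not be used.

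**Conclusion.** The point holds in a limited form. As worded, the primary outcome can score a trial-generated kit return as linkage, and a difference in uptake between arms would then carry over into the primary comparison. Under the assumptions above, the spurious difference is about 0.5 to 1.8 points for uptake of 40% v 50% and about 0.9 to 3.6 points for 40% v 60%, with f from 5% to 20%, against a design difference of 5 points. The true size cannot be fixed from the Protocol.

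A reader might go further and infer that the primary result could not be read as linkage at all. The Protocol does not support that. The bias needs both a difference in uptake and facility returns that are reported as attendance. The secondary survey outcome of linkage to PSI outreach is also untouched by facility drop-offs, so a rise in the primary outcome without a rise in that one would be visible. This is something that should be fixed because the remedy is nearly free and the information cannot be recovered later; it does not undermine the design.

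**What to change.** 1. Add an item to the self-administered tablet questionnaire on the purpose of each facility visit, with 'only to return a used kit' as one of the answers.
2. State in the primary outcome definition that a visit made only to return a kit does not count as attendance, in either arm, and bring the wording of Figure 2 into line.
3. Read the primary result alongside the existing secondary outcome of linkage to PSI outreach.

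The cost is one extra question, one sentence and a slightly lower measured rate. Moving the boxes away from health facilities is optional and is not needed for this fix.

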## 4.2.4 Description of study interventions

## Incentives for CBDs

During training, CBDs in communities that have been randomised to CBD incentives for linking selftesters to post-test services will be told that they will get a stipulated amount of money (20c) for each self-tester who attends the PSI outreach site after testing. Upon attendance at outreach sites, all clients who report having self-tested will be asked to show their self-completed appointment card (which bears the CBD identity number) to PSI staff. Staff will keep a log of clients that attend according to CBD in order to facilitate payment of the CBD. If a client has not brought their appointment card, they will be asked to provide the name of the CBD who supplied the self-test kit, which will be verified with CBD kit distribution records in that area before the CBD is credited with the attendance.

## Referral of clients confirmed as HIV positive

Following confirmatory HIV testing and counselling at the outreach site, PSI will conduct point of care CD4 testing for HIV positive clients. HIV positive clients will be referred to local HIV treatment centres

by using a paper referral slip as per existing PSI procedures. A carbon copy of the referral slip will be retained by PSI staff. HIV positive clients will be encouraged to take their referral slip to the referral treatment and care centre where staff will have been trained to keep all referral documentation from the referring organisation (in this case PSI) and mark the source of referral during patient registration, as per existing procedures.

## Evaluating the effect of HIVST and CBD incentivisation on ART initiations in the study districts

Using a standard data collection form (Appendix 3), data on monthly number of ART initiations will be abstracted from records of all health facilities in each study district for the following periods:

- Six months before distribution of HIVST test kits is started
- During period of HIVST kit distribution
- Three months after HIVST kit distribution has been completed

## 4.2.5 Qualitative study on linkage

From three months after distribution of test kits, in-depth interviews will be conducted with

- 20-30 clients who have tested using an HIV self-test
- 20-30 PSI health care workers
- 20-30 CBDs
- 20-30 Public sector health care workers,

to explore the barriers and facilitators to linkage to HIV treatment and prevention services and VMMC services. Participants will be asked about barriers and facilitators to linkage, perceived effect of HIV self-testing on autonomy, responsibility, empowerment and abandonment in terms of linkage to prevention and care services.

These qualitative studies will be conducted in the 8 study communities (two from each arm) that will be designated for process evaluation (Section 4.2.9 below), except for IDI with PSI health care workers where attempts will be made to ensure representation of PSI teams from all provinces.

20-25 key informants from Ministry of Health and Child Care, other providers of HIV testing and counselling services and community leaders will also be interviewed about this and how communities can lead distribution of self-test kits while ensuring good linkage to prevention and care services.

## Recruitment of Clients

HIV positive participants will be purposively selected from the eight study communities to ensure representation of those who did/did not link to PSI outreach sites and those who did/did not link to government ART services. The following sorts of clients will be eligible for the study

- At least 16 years old
- Having lived in the study community at the time kit distribution was done
- Self-tested HIV positive (based on self-reports at PSI outreach site or household survey)
- Willing and able to give written informed consent for participation (in addition parental consent will be required for individuals who are less than 18 years old)

